## 8 STUDY DESIGN

### 8.1 Overall study design and schedule of events

This is a two-arm, double-blind, randomized, placebo-controlled Phase 2a study evaluating the safety, tolerability, and preliminary efficacy of up to 2 mg/day of NLX-112 versus placebo in patients with moderate to severe L-DOPA induced dyskinesia (LID) in Parkinson's disease (PD). NLX-112 will be up-titrated to either 2 mg/day (1 mg BID) or to the highest well-tolerated dose less than 2 mg/day over 4 weeks, maintained at the well-tolerated dose for an additional 2 weeks, and then down-titrated over 2 weeks. An overview of the study design is shown in Figure 1.

Patients will report to the study clinic for a screening visit (Visit 1), followed by a baseline visit on Day 1 (Visit 2) where patients will be randomized and begin treatment. Two remote safety visits over telephone (Days 7 and 49 [Visit 3 and Visit 8]) will be conducted. Once treatment has commenced, there will be 2 in-person safety visits to the clinic (Days 14 and 21 [Visit 4 and Visit 5]), 2 in-person efficacy visits to the clinic (Days 28 and 42 [Visit 6 and Visit 7]) and one follow-up in-person final safety visit (Day 70 [Visit 9]). In total, patients will report to the clinic for 7 in-person visits. Patients entering the study will be randomized in a 2:1 ratio (16:8 patients) to receive either NLX-112 or placebo.

[figure not shown]
At Visits 2, 6 and 7, efficacy assessments will start 30 minutes after the patient has taken 150% of his or her regular L-DOPA dose, when the patient is ON and experiencing typical dyskinesia.

The order of assessments at each visit is specified in Section 8.2.

A PD Home Dyskinesia Diary (electronic) will be completed by the patients and/or caregiver with concordance in ON time with dyskinesia between study staff and patient. Two consecutive 24-hour diaries will be completed prior to randomization (baseline, Visit 2) and prior to the clinic visits on Days 28 and 42 (Visits 6 and 7).

A wearable dyskinesia assessment device will be used to monitor dyskinesias during a 2-day period prior to the baseline visit (Day 1, Visit 2) and a 2-day period prior to the clinic visits on Days 28 and 42 (Visits 6 and 7, respectively).

Blood will be collected for possible NLX-112 plasma concentration measurements on Days 14, 21, 28, 42 and 70 (Visits 4, 5, 6, 7 and 9).

**Figure 1** Overview of study design

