### 5.2 Sample size calculation

No formal sample size calculation has been performed. The sample size of 24 patients is considered sufficient to evaluate the primary objective and to allow for a preliminary efficacy evaluation.

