## 5.7 Significance level

All hypothesis testing will be two-sided, using a 5% significance level ( $\alpha=0.05$ ).

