**Table 2 Changes in the planned statistical analyses**

Change category	Timing of change	Description of change	Reason for change	Responsible for change
Change in the SAP compared to the CSP	Prior to DBL	The safety analysis set has been omitted.	Safety evaluations based on FAS is considered sufficient.	[name]
Change in the SAP compared to the CSP	Prior to DBL	The Chi2 test for the ON Time Without Troublesome Dyskinesia analysis has been replaced with a linear mixed model approach.	The CSP prescribes that a chi-square test be performed for ON Time Without Troublesome Dyskinesia data for the whole study period. As there are multiple measurements per patient and visit, it is not clear how this can be implemented. Hence a shift to a mixed model approach has been adopted.	[name]
Change in the SAP compared to the CSP	Prior to DBL	Wilcoxon signed rank tests have been replaced with linear mixed modeling with a non-parametric back-up plan should model assumptions fail.	In order to use all available data in the same model, potentially resulting in higher power in the analyses, a mixed model approach has been adopted instead.	[name]
Change in the SAP compared to the CSP	Prior to DBL	The Kinesia 360 wearable dyskinesia assessment system and PD home dyskinesia diary data for up to 4*24 hours prior to Visit 6 and 7 is included in the analyses.	The CSP prescribes data from only up to 2*24 hours to be used in Kinesia 360 wearable device and home diary analyses. However, using the cut-off point of 4*24 hours prior to Visit 6 and 7 respectively was deemed medically acceptable, whereas at the same time minimizing the amount of missing data in the corresponding analyses.	[name]

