### 9.2 Analysis of secondary endpoints

#### 9.2.1 *Statistical inferential analysis of efficacy endpoints*

Absolute change from baseline in efficacy endpoints (secondary and exploratory endpoints) will generally be analysed using a linear mixed model with treatment, visit and the interaction

treatment\*visit as fixed categorical effects and subject within treatment as a random effect. The baseline value of the dependent variable will be included in the model as a continuous covariate, to account for possible differences in change from baseline outcomes due the starting baseline level. Visit will be modelled as a repeated effect. Kenward-Roger's approximation for degrees of freedom will be used.

Providing a significant type III F-test for the interaction effect treatment\*visit, differences between least square estimates of NLX-112 and placebo for the same visit (i.e. from the interaction term treatment\*visit, where visit is the same for both NLX-112 and placebo) will be estimated and the corresponding p-value will be presented in tables. In addition, differences between least square estimates of each post-baseline visit and baseline for NLX -112 and placebo respectively (i.e. from the interaction term treatment\*visit, where treatment is the same for the post-baseline and the baseline visit) will be estimated and the corresponding p-value will be presented in tables.

The model proposed above will be used for FAS and is valid, as long as the underlying data is missing at random (MAR). As a sensitivity analysis, the model will also be run for PPS, serving as a validity check for the main FAS analysis. The sensitivity analysis will be a complete case analysis, i.e., only patients with no missing data for the dependent variable will be used.

Model diagnostics, for example Shapiro-Wilk's test for a normally distributed residual term and Leven's test for the homoscedasticity assumption of the residual term as well as Q-Q plots and plotting residuals vs. predicted values, will be performed. If model assumptions are deemed to be violated, an attempt will be made to transform the dependent variable in order to fulfil model diagnostics.

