A box-cox model will be used to find the most appropriate transformation of data. Lambda values between -3 and 3 will be tested using increments of 0.25. The dependent variable will be transformed accordingly, and the linear mixed model rerun on transformed data. Subsequently, the same model diagnostics as described above will be performed. If model assumptions are deemed to be violated, the linear mixed model approach will not be further pursued for the corresponding dependent variable.

If transforming data according to the above method fails, the analysis will be done using non-parametric methods. A Wilcoxon rank sum test will be used to assess statistically significant differences between active treatment and placebo for relative change from baseline in efficacy endpoints for all post-baseline visits respectively. Furthermore, a Wilcoxon signed rank test will be performed for each post-baseline visit and baseline for NLX -112 and placebo respectively to assess statistically significant differences between each post-baseline visit and baseline for each treatment separately.

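### The non-parametric fallback in SAP 9.2.1 drops the baseline covariate and tests relative change, which mis-corrects chance imbalance at 16 v 8 and is undefined when baseline is 0

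*SAP*

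**What the plan says.** SAP 9.2.1 analyses absolute change with a linear mixed model. On baseline it says: "The baseline value of the dependent variable will be included in the model as a continuous covariate". The reason it gives is that the change may depend on the level at which a patient starts.

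The fallback is a last resort, applied one dependent variable at a time. The model must fail its diagnostics, a Box-Cox transformation is then tried, the same baseline-adjusted model is rerun, and only a second failure ends that route: "If transforming data according to the above method fails, the analysis will be done using non-parametric methods". The between-arm test then becomes: "A Wilcoxon rank sum test will be used to assess statistically significant differences between active treatment and placebo for relative change from baseline". It is done separately at each post-baseline visit, with signed-rank tests within each arm. No covariate or stratification is named, and the move from absolute to relative change is not explained.

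The secondary and exploratory efficacy sections (9.2.2 to 9.3.5) refer back to 9.2.1, so the rule can apply to any of them. Table 2 of the SAP records the arrangement: "Wilcoxon signed rank tests have been replaced with linear mixed modeling with a non-parametric back-up plan should model assumptions fail".

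**The concern.** Badly behaved residuals do not stop the change from depending on baseline. The SAP's own reason for the covariate therefore still applies when the fallback is used, yet the covariate goes. An endpoint that fails diagnostics would be compared without adjustment while its neighbours in the same report are adjusted.

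The scales most likely to reach the fallback are short and bounded at zero: KPPS items run 0–12, each HADS subscale 0–21 and ICIQ-OAB 0–16 (Protocol 11.4.1, 11.4.3, 11.4.4). A patient with no symptom in a domain scores 0 at baseline and has no relative change. The SAP has no rule for this, so such patients would drop out of the test. CGI-C is already a change rating and has no relative change from baseline.

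At stake are power that costs nothing to recover, and between-arm p-values that lean on chance baseline differences in a trial with 8 placebo patients.

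**Working it through.** **Inputs from the documents.** Allocation: "randomized in a 2:1 ratio (16:8 patients) to receive either NLX-112 or placebo" (Protocol 8.1). Level: "All hypothesis testing will be two-sided, using a 5% significance level" (SAP 5.7). There is no planned power figure to reproduce: "No formal sample size calculation has been performed" (SAP 5.2).

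**Assumptions.** Correlation ρ between baseline and visit value of 0.3 to 0.8; effect of 1 baseline SD unless stated; no dropout; one visit at a time.

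**Step 1: why change is not adjustment.** With equal variances (SD = 1), absolute change has variance 2(1−ρ), and the covariate-adjusted outcome has 1−ρ². The ratio is (1+ρ)/2, which is 0.75 at ρ 0.5, a 25% reduction. This algebra is for absolute change. Relative change has no such simple form and needs simulation.

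**Step 2: chance imbalance.**
- The SE of the baseline difference is √(1/16 + 1/8) = 0.433 SD. So P(|difference| > 0.5 SD) is about 25%, and P(|difference| > 0.8 SD) about 6% (0.8/0.433 = 1.85).
- An imbalance m shifts the absolute-change contrast by −(1−ρ)m. Ignoring baseline altogether shifts it by +ρm.
- For m = 0.5 SD: at ρ 0.5 the shifts are −0.25 and +0.25 SD; at ρ 0.8 they are −0.10 and +0.40 SD.
- The imbalance is therefore corrected at the wrong slope, and the error shrinks as ρ rises.
- Simulated null rejection of the relative-change rank-sum test at ρ 0.5 (baseline CV 0.25) is 2.5%, 4.8% and 9.5% for m = 0, 0.5 and 0.8 SD. At m = 0.8 SD and ρ 0.8 it is 7.3%. An adjusted rank test stays at 4.0–5.8% in these settings. Averaged over imbalances, the planned test is at or just below 5%.

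**Step 3: power, planned test v adjusted rank test.** The fair comparator is a rank test that uses baseline, because normal-theory ANCOVA has already been ruled out when the fallback starts. Simulation at 16 v 8, 4,000 trials per cell (Monte Carlo SE at most √(0.25/4000) = 0.8 points per power):

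| Scores | ρ | Rank-sum, relative change | Rank ANCOVA | Difference |
|---|---|---|---|---|
| Normal | 0.3 | 47% | 60% | +13 |
| Normal | 0.5 | 60% | 67% | +7 |
| Normal | 0.7 | 80% | 80% | 0 |
| Normal | 0.8 | 93% | 89% | −4 |
| Log-normal | 0.3 | 43% | 59% | +16 |
| Log-normal | 0.5 | 56% | 67% | +11 |
| Log-normal | 0.7 | 78% | 80% | +2 |
| Log-normal | 0.8 | 91% | 90% | −1 |

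Null rejection for rank ANCOVA was 4.6–5.3%. Repeat runs with other seeds and score models put the difference at 13–17 points at ρ 0.3, 6–8 (normal) or 11–13 (skewed or zero-heavy) at ρ 0.5, 0–3 at ρ 0.7 and −1 to −4 at ρ 0.8.

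**Step 4: scales with many zeros.** With about 16% of baselines at 0, those patients are lost to the relative-change test, and the adjusted test gains 7–14 points at every ρ tried.

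**Step 5: sensitivity at ρ 0.5.** For effects of 0.8 to 1.2 SD the gain is 7 down to 4.5 points with normal errors, 16 down to 7 with skewed errors and 10 down to 3 with heavy-tailed (t, 3 df) errors. If the effect on log-normal scores is additive instead of multiplicative, the planned test has 85% and rank ANCOVA 82%: no gain. That case is illustrative only, since the model allows negative scores.

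**The case against.** The best reply is that this is a plain, robust last resort, close to the Wilcoxon tests in the protocol, reached only after two failures of an adjusted model, in a study whose efficacy tests are exploratory and unadjusted for multiplicity (SAP 5.8). Much of that stands. It limits how often the point bites and how much it matters. It does not explain why a baseline that has been collected should be dropped, or what to do with a zero.

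A reader might infer three stronger things that the documents do not support.

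- **That the fallback has less power than the main model.** SAP 9.2.1 allows the visit-wise treatment comparison only under a condition: "Providing a significant type III F-test for the interaction effect" of treatment by visit. No such condition is stated for the fallback. With ρ 0.5, a 1 SD effect at Day 42 and the two post-baseline visits as the visit levels, the gated model has 3% power if the Day 28 effect is equal, and 10–34% if it is 0.5–0.7 SD. The ungated rank-sum test on relative change has 58–59%.
- **That imbalance is left uncorrected, or that type I error is inflated.** Baseline is used, at the wrong slope. The excess appears only conditionally, in trials with a large imbalance.
- **That one figure gives the power loss.** It depends on ρ, effect size and score shape, none of which is in the documents. At ρ 0.8 its sign reverses on scales without zeros.

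It is also fair to say that a rank ANCOVA of the visit value departs from a change score. Conditional on baseline it still asks whether the arms differ at that visit, and the planned fallback has itself already moved from absolute to relative change.

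**Conclusion.** The point holds as a conditional weakness. For any endpoint that reaches the fallback, the between-arm test loses the adjustment the SAP itself says is needed, mis-corrects chance imbalance, and has no value for patients with a baseline of 0.

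The size rests on an assumed 1 SD effect. Against the planned test, a baseline-adjusted rank test gains about 13–17 power points at ρ 0.3, 6–13 at ρ 0.5 and 0–3 at ρ 0.7. It loses about 1–4 at ρ 0.8, though a gain remains on zero-heavy scales. An additive effect on skewed scores can remove the gain. Because the efficacy tests are exploratory, the consequence is moderate: worth changing, but not a threat to the primary safety objective.

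**What to change.** In SAP 9.2.1, replace the between-arm fallback test with a rank ANCOVA at each post-baseline visit. Rank the visit values and the baseline values across both arms, then test the treatment term in a linear model of ranked visit value on ranked baseline and treatment, two-sided at 5%. State that patients with a baseline of 0 are kept. Retain the unadjusted rank-sum test for CGI-C only, applied to the rating itself. Update the back-up entry in Table 2 and the table footnotes to match, before the treatment code is broken.

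The cost is a few lines of SAP text and SAS code, with no new data. The downside is a loss of about 1–4 power points if the baseline correlation is about 0.8 or higher on scales without many zeros. A rank-sum test on residuals from a pooled regression of absolute change on baseline loses at most about 3 points, and only against relative change on skewed scores, but it relies on a linear regression of the kind just set aside.

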### **11.4 Assessments related to exploratory endpoints**

#### **11.4.1 *King's Parkinson's Disease Pain Scale (KPPS)***

The KPPS is a rater-interview-based scale conducted with the patient and caregiver (if available). It is a 14-item scale covering 7 domains of pain:

- Musculoskeletal pain
- Chronic pain
- Fluctuation-related pain
- Nocturnal pain
- Orofacial pain

- Edema/swelling; discoloration
- Radicular pain

Each item is scored by severity (0 - 3; none to very severe) multiplied by frequency (0 - 4; never to all the time), for an item sub score of 0-12, resulting in a total score from 0 to 168. Ratings are based on the previous month, or in the case of this study, the intervening period since the previous clinic visit (about 3 weeks). Treatment effects will be analyzed as change from baseline for total score and for individual pain domains.

For timing of assessments, refer to Table 8.1-1.

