## 5.9 Handling of dropouts, missing data and outliers

Outliers will be included in summary tables and listings and will not be handled separately in any analyses. Generally, no imputation of data will be performed. However, in case of a substantial amount of missing data, judged to affect analyses conclusions related to secondary and exploratory endpoints, imputation methods might be considered or alternative analysis approaches, for example analysing mean scores instead of total scores.

In case of missing start and stop times of AEs that cannot be investigated further, missing data will be imputed according to a worst-case scenario. That is, start time will be imputed as the closest time point post first intake of IMP and end time as 23:59, resulting in the longest possible treatment emergent duration of the AE.

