### 10.2.3 Secondary endpoint(s)

#### 10.2.3.1 Unified Dyskinesia Rating Scale (UDysRS) total score

**Table UD 1 UDysRS total score for all Parts (Full analysis set)**

Result category	Assessment timepoint		NLX-112 (N=XX)	Placebo (N=XX)	Total (N=XX)
Measured value	[Assessment timepoint 1]	n	xx	xx	xx
		Mean (SD)	x.xx (x.xx)	x.xx (x.xx)	x.xx (x.xx)
		Median (Min, Max)	x.xx (x.x, x.x)	x.xx (x.x, x.x)	x.xx (x.x, x.x)
	[Assessment timepoint 2]	n	xx	xx	xx
		...	...	...	...
Absolute change from baseline	[Assessment timepoint 2]	n	xx	xx	xx
		Mean (SD)	x.xx (x.xx)	x.xx (x.xx)	x.xx (x.xx)
		Median (Min, Max)	x.xx (x.x, x.x)	x.xx (x.x, x.x)	x.xx (x.x, x.x)
	[Assessment timepoint 3]	LMM a p-value	xxxxx b	xxxxx c	xxxxx d
		n	xxxxx	xxxxx	xxxxx
		...	...	...	...
Relative change from baseline (%)	[Assessment timepoint 2]	n	xx	xx	xx
		Mean (SD)	x.xx (x.xx)	x.xx (x.xx)	x.xx (x.xx)
		Median (Min, Max)	x.xx (x.x, x.x)	x.xx (x.x, x.x)	x.xx (x.x, x.x)
	[Assessment timepoint 3]	n	xxxxx	xxxxx	xxxxx
		...	...	...	...

a) Linear mixed model (LMM) with treatment, visit and the interaction treatment\*visit as fixed categorical effects and subject within treatment as a random effect. The baseline value of the dependent variable has been included in the model as a continuous covariate. Kenward-Roger's approximation for degrees of freedom will be used.

b) p-value for the difference between NLX-112 at the assessment timepoint and at baseline.

c) p-value for the difference between placebo at the assessment timepoint and at baseline.

d) p-value for the difference between NLX-112 and placebo absolute change from baseline at the assessment timepoint.

Data based on the Full analysis set. The session marked as most severe for Part III and IV have been used. For Part III, the highest score for each individual questionnaire item has been used. All UDysRS item scores for Part I, II, III and IV have been summarized pre patient and assessment timepoint and used as input data to the table. N: Number of observations. SD: Standard deviation. NC: Not calculated - number of evaluable observations less than 3. NA: Not available - no evaluable observations. SAS program: [PROGRAM NAME].sas. Run by: [USERNAME] YYYY-MM-DDTHH:MM:SS. Data extracted at: YYYY-MM-DDTHH:MM:SS

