Produce the table above for PPS as well, providing there is any de facto difference between the analysis sets. If the LMM is performed using transformed data, insert a footnote about this as well. If the LMM approach is dropped in favour of non-parametric tests, update the table and footnotes accordingly.

**Table UD 2 UdysRS total score for Part III and IV – Most severe assessment session and highest questionnaire item score (Full analysis set)**

Use the same format as for Table UD 1. Produce the table above for PPS as well, providing there is any de facto difference between the analysis sets. If the LMM is performed using transformed data, insert a footnote about this as well. If the LMM approach is dropped in favour of non-parametric tests, update the table and footnotes accordingly.

**Table UD 3 UdysRS total score for Part III and IV – Average of assessment sessions and highest questionnaire item score (Full analysis set)**

Use the same format as for Table UD 1, but update the explanatory footnote to reflect the content of the table. Produce the table above for PPS as well, providing there is any de facto difference between the analysis sets. If the LMM is performed using transformed data, insert a footnote about this as well. If the LMM approach is dropped in favour of non-parametric tests, update the table and footnotes accordingly.

**Table UD 4 UdysRS total score for Part III– Most severe assessment session and sum of questionnaire item scores (Full analysis set)**

Use the same format as for Table UD 1, but update the explanatory footnote to reflect the content of the table. Produce the table above for PPS as well, providing there is any de facto difference between the analysis sets. If the LMM is performed using transformed data, insert a footnote about this as well. If the LMM approach is dropped in favour of non-parametric tests, update the table and footnotes accordingly.

**Table UD 5 UdysRS total score for Part III– Average of assessment sessions and sum of questionnaire item scores (Full analysis set)**

Use the same format as for Table UD 1, but update the explanatory footnote to reflect the content of the table. Produce the table above for PPS as well, providing there is any de facto difference between the analysis sets. If the LMM is performed using transformed data, insert a footnote about this as well. If the LMM approach is dropped in favour of non-parametric tests, update the table and footnotes accordingly.

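### The between-arm rank-sum fallback tests relative change while the model it replaces tests absolute change, and relative change is undefined at a zero baseline

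*SAP*

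**What the plan says.** **Main model (SAP 9.2.1).** "Absolute change from baseline in efficacy endpoints (secondary and exploratory endpoints) will generally be analysed using a linear mixed model", with the baseline value as a covariate.

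**Planned display (SAP 10.2.3.1, Table UD 1).** Footnote d defines the between-arm result as the "p-value for the difference between NLX-112 and placebo absolute change from baseline at the assessment timepoint". Percent change is a separate block of the same table.

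**Fallback (SAP 9.2.1).** If the diagnostics fail and the Box-Cox transformation does not repair them, two non-parametric tests follow. The between-arm rank-sum test assesses "statistically significant differences between active treatment and placebo for relative change from baseline in efficacy endpoints". Within each arm, "a Wilcoxon signed rank test will be performed for each post-baseline visit and baseline".

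**Display after a fallback.** The note to Table UD 1 says: "If the LMM approach is dropped in favour of non-parametric tests, update the table and footnotes accordingly".

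**Change log (SAP section 6, Table 2).** "Wilcoxon signed rank tests have been replaced with linear mixed modeling with a non-parametric back-up plan should model assumptions fail". The entry names neither the rank-sum test nor relative change.

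**Missing values (SAP 5.9).** "Generally, no imputation of data will be performed". Imputation or other approaches may be considered if missing data are substantial. Zero baselines are not mentioned.

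**Score ranges.** The KPPS items give a range "resulting in a total score from 0 to 168" (Protocol 11.4.1). HADS subscores, ICIQ-OAB, ESS (Protocol 11.4.3 to 11.4.5) and PDQ39 dimensions (SAP 9.3.2) also start at zero.

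**The concern.** A fallback should answer the same question as the analysis it stands in for, by a method that needs fewer assumptions. Here the question changes as well. The protocol's endpoints (7.2.1 and 7.3.1) are plain changes from baseline. Where the protocol wants percent change, for vital signs and laboratory data, it says so (17.5.3 and 17.5.6).

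Relative change also divides by the baseline score. A patient with no pain, no bladder symptoms or no depressive symptoms at baseline has no relative change. With no rule in the SAP, that patient leaves the between-arm test, in a trial with about 8 patients on placebo (SAP 4.3). Any rule would then have to be improvised, possibly with the treatment codes open.

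**Working it through.** There is no planned power or error rate to reproduce, because no formal sample size calculation was made (SAP 5.2).

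**1. Quantities side by side.** With D = post − baseline and R = 100 × (post − baseline) / baseline:

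| Analysis | Quantity |
|---|---|
| Mixed model, 9.2.1 | D |
| Table UD 1, footnote d | D |
| Within-arm signed-rank fallback | ranks of D (by construction of the test; the SAP does not use the word absolute) |
| Between-arm rank-sum fallback | R |

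**2. D and R can order patients differently.** A fall from 60 to 48 is D = −12, R = −20%. A fall from 16 to 8 is D = −8, R = −50%. The first patient improves more on D, the second on R.

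**3. Where a zero baseline is possible.** Variables sent to 9.2.1: UDysRS 5, ON time 1, UPDRS 2, CGI-C 1, Kinesia 1, KPPS 8, PDQ39 9, HADS 2, ICIQ-OAB 1, ESS 1, in total 31. Eligibility (Protocol 9.4 and 9.5) sets no minimum on KPPS, PDQ39, HADS, ICIQ-OAB or ESS: 8 + 9 + 2 + 1 + 1 = 21. ON time without troublesome dyskinesia is a share of awake records (SAP 9.2.3). The entry criterion requires troublesome ON time but no other ON time, so this share can be zero too: 21 + 1 = 22. Possible does not mean likely; a zero PDQ39 total would be unusual in these patients. A zero UPDRS combined score is excluded by the entry requirement on item 33, and a zero UDysRS total is unlikely. For those two, only the change of quantity matters.

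**4. CGI-C.** Only CGI-S is rated at baseline (Protocol Table 8.1-1, footnote 12), so R cannot be formed. Nor can the model's baseline covariate.

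**5. Patients left.** The share s of zero baselines is not in the documents; 10%, 25% and 50% are assumed. Expected number left is 24(1 − s), and 8(1 − s) on placebo. The chance of losing at least one placebo patient is 1 − (1 − s)^8.

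| s | Left of 24 | Left of 8 | At least one placebo lost | 4 or fewer placebo left |
|---|---|---|---|---|
| 10% | 21.6 | 7.2 | 57% | 0.5% |
| 25% | 18 | 6 | 90% | 11% |
| 50% | 12 | 4 | 99.6% | 64% |

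**6. Rejection rates on a scale with zeros.** Simulation, all inputs assumed: 0–24 scale, non-zero baselines gamma(4, 2) rounded and limited to 1–24, residual SD 2, 16 versus 8, two-sided rank-sum test at 5%, 3,000 trials per cell (standard error at most √(0.25/3000) = 0.9 points). Zero-baseline patients are dropped from the R test only. Entries are D versus R, in percent.

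| s | Additive effect of 2 | Effect 30% of baseline | No effect |
|---|---|---|---|
| 0% | 55.0 v 48.5 | 63.7 v 53.6 | 4.5 v 4.7 |
| 10% | 48.9 v 43.6 | 53.2 v 48.1 | 4.0 v 4.1 |
| 25% | 43.1 v 36.2 | 35.0 v 39.0 | 3.9 v 4.0 |
| 50% | 35.2 v 20.6 | 17.3 v 22.2 | 4.3 v 3.1 |

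**7. UDysRS, no zeros.** Assumed additive effect 10 and residual SD 9; the slope is that of the post score on baseline.

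| Baseline mean/SD | Slope 1: D v R (trials disagreeing at 5%) | Slope 0.7: D v R (trials disagreeing at 5%) |
|---|---|---|
| 40/15 | 66 v 62 (13.5) | 55 v 59 (12.3) |
| 40/10 | 66 v 63 (8.8) | 60 v 62 (8.2) |
| 30/15 | 64 v 58 (17.3) | 55 v 58 (14.5) |

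With no effect, both tests reject in 4.2–5.0% of trials and disagree in 1.4–2.9%. Either test may be ahead, and with a real effect the choice of scale decides significance in roughly 8–17% of trials.

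**The case against.** Relative change is specified openly and in advance, and it can be defended. The mixed model adjusts for baseline; a rank-sum test has no covariate, and dividing by baseline partly makes up for that, which absolute change does not. This stands as a reason someone might have had. The SAP does not state it, and it does not help where the ratio is undefined.

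A reader might infer four stronger charges. The documents do not support them.

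- *Patients vanish silently.* They do not. The relative-change rows in the SAP table shells print n by arm and visit, so a loss would show. SAP section 10 also withholds tables when data or variability are insufficient, which might remove extreme cases.
- *Table UD 1 contradicts the fallback.* Its footnotes describe the mixed-model p-values, and the SAP orders them updated after a fallback. A row mixing two quantities is a possible outcome, not a written one. What stands is the shift between main analysis and fallback.
- *CGI-C fails because of relative change.* The gap is wider: the main model's baseline covariate is missing too. Table CG 1 treats the rating itself as the change, so testing the rating is the natural reading, though the fallback text does not say so.
- *The switch costs power or inflates false positives.* Neither holds in general, as steps 6 and 7 show.

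The Box-Cox step states no shift constant although a change score can be zero or negative. That may make the fallback easier to reach, but it is a separate matter.

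**Conclusion.** The point holds, as a minor one. The between-arm fallback changes the tested quantity from absolute to relative change without a stated reason. As written, it cannot be computed for zero-baseline patients on any of 22 outcome variables where a zero is possible, or for CGI-C at all.

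The reach is limited. The model diagnostics must fail, and then the transformation. Only secondary and exploratory endpoints are involved, and the SAP calls significant findings indicative (5.1) and its efficacy tests explorative (5.8). The text comparison rests on no assumption except the standard construction of the signed-rank test. The patient losses and rejection rates rest entirely on assumed zero shares and score distributions and show direction only. The case is the unexplained change of quantity and the undefined test, not power.

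**What to change.** In SAP 9.2.1, run the between-arm rank-sum fallback on absolute change from baseline. For CGI-C, run it on the rating itself, as Table CG 1 already does, and say what, if anything, serves as its baseline covariate in the main model. Keep percent change as a descriptive row without a p-value. In Table 2, name the rank-sum test and the quantity it tests. Make the change before unblinding.

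The drafting cost is a few SAP sentences and one table entry. The statistical cost is that the percent-change p-value is lost and the fallback no longer scales for baseline. Power can then be a few points lower when the effect is proportional to baseline (35.0% v 39.0% and 17.3% v 22.2% in step 6) or when the slope on baseline is below 1 (step 7). In a further run with a lognormal baseline (coefficient of variation 0.8) and both effect and noise proportional to it, the gap was 64.4% v 74.9%, or 10.5 points. Type I error is unaffected. If the sponsor prefers relative change for such reasons, the SAP should state the reason and add a zero-baseline rule; the fallback would then still test a different quantity from the main model.
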